8.1.3.1.3 NRS-11 (adult cohort only)

The NRS-11 is a self-reported segmented 11-point numeric scale that assesses pain intensity (Hawker et al 2011). It consists of a horizontal line with 0 representing "no pain" at the left end of the line and 10 representing "worst pain you can imagine" at the right end. Subjects are asked to select the one number from 0 to 10 that best describes their worst pain over the past 7 days for the following: 1) physician selected target-tumour pain, 2) overall tumour pain, and 3) overall pain. It takes less than 1 minute to complete. The target tumour will be selected by the physician from a list of body locations in Table 9. The NRS-11 is recommended as a core outcome measure of pain intensity for clinical studies (Dworkin et al 2005; Wolters et al 2013). Adult subjects only will complete the NRS-11 for this study.

1	Head	16	Pelvic area
2	Еуе	17	Genitalia
3	Face	18	Upper arm
4	Ear	19	Forearm
5	Mouth/Tough	20	Hand
6	Neck (Front)	21	Thigh/Upper leg
7	Neck (Back)	22	Lower leg
8	Shoulder	23	Foot
9	Chest		
10	Armpit		
11	Flank		
12	Back (Upper)		
13	Back (Lower)		
14	Abdomen		
15	Buttock		

8.1.3.1.4 Pain Interference Index

The PII is a 6-item measure that assesses the degree to which pain has interfered with daily activities in the past week. This measure was developed in Sweden and validated in Swedish with a group of children and adolescents with longstanding idiopathic pain (Wicksell et al 2009). The PII was translated into English and the wording was modified to make it more readable and to shorten the time frame to 1 week. A parallel parent version of the PII was also created. Results of validation studies in children with NF1 and their parents indicate that the internal consistency and construct validity of the PII are good. These data support the use of the PII to assess pain interference in youths with NF1 and PNs (Martin et al 2015). PII has also been validated for use in adults (Kemani et al 2016). For this study, adults and children from 8 to 17 years of age will complete self-reported PII, and parents or the legal guardian of children from 5 to 17 years of age will complete the parent proxy PII.

8.1.3.1.5 Pain medication survey (all subjects)

A pain medication survey will be used to ensure that potential pain palliation is not the result of increased usage of analgesics (Basch et al 2014). Information on daily and as-needed pain medications will be collected, including dates, pain medication name, dose and frequency. The pain medication survey will not be collected through the eCOA tablet, but with a paper version.

8.1.3.2 Health-related quality of life

The effect of selumetinib on HRQoL will be evaluated using the PedsQL (paediatric cohort) and EORTC QLQ-C30 and PlexiQoL (adult cohort).

8.1.3.2.1 PedsQL (paediatric cohort)

The PedsQL Core version 4 is a widely accepted measure for assessing HRQoL in paediatric subjects (Varni et al 2001) and will be used for the paediatric cohort.

The PedsQL 4.0 Generic Core Scales are multidimensional child self-reported and parent proxy-reported scales to assess HRQoL. PedsQL is a brief standardised paediatric HRQoL scale with good reliability and validity, which includes both generic and disease-specific modules. It consists of a 23-item core measure of global HRQoL that has 4 subscales: physical functioning, emotional functioning, social functioning, and school functioning.

The PedsQL Core version 4 has been developed in age-specific versions. In this study, the self-reported versions are for subjects aged 5 to 7 years, 8 to 12 years, and 13 to 17 years. In addition, the corresponding parent-reported versions will also be included. For subjects 3 to 4 years of age, only the parent-reported version will be included. Acute versions of the PedsQL questionnaires (7-day recall period) will be used in this study. The questionnaire takes approximately 5 to 10 minutes to complete.

8.1.3.2.2 EORTC QLQ-C30 and PlexiQoL (adult cohort)

For the adult cohort, the validated measures EORTC QLQ-C30 (Aaronson et al 1993) and PlexiQoL (Heaney et al 2019) will be used for assessments of HRQoL.

The EORTC QLQ-C30 was developed by the EORTC Quality of Life Group in 1993. It consists of 30 items and measures cancer patients' functioning (HRQoL) and symptoms for all cancer types (Aaronson et al 1993). Questions can be grouped into 5 multi-item functional scales (physical, role, emotional, cognitive, and social); 3 multi-item symptom scales (fatigue, pain, and nausea and vomiting); a 2-item global HRQoL scale; 5-single items assessing additional symptoms commonly reported by cancer patients (dyspnoea, loss of appetite, insomnia, constipation, diarrhoea) and 1 item on the financial impact of the disease.

The PlexiQoL was developed through funding by The Neurofibromatosis Therapeutic Acceleration Program. It may be considered ancillary to the EORTC QLQ-C30. The impacts captured by this instrument, including shame/discomfort/embarrassment, negative body image, and impact on role, are not captured by the EORTC QLQ-C30. The European Medicines Agency issued a letter of support (January 2018) for consideration of the PlexiQoL for use in clinical studies (European Medicines Agency 2018).

8.1.3.3 Physical functioning

PROMIS is a set of person-centred measures that evaluates and monitors physical, mental, and social health in adults and children. It can be used with the general population and with individuals living with chronic conditions (PROMIS website).

The PROMIS Physical Functioning Scales assess the domains of Mobility and Upper Extremity Function and include mobility items such as "I can walk upstairs without holding on to anything" and upper extremity items such as "I can button my shirt or pants." Parent proxy items are parallel to child items. PROMIS paediatric 8-item short forms show good psychometric characteristics after large-scale testing (DeWitt et al 2011). The paediatric parent proxy physical functioning scales also can be used for children ages 5 to 7 years (Varni et al 2014).

Self-reported short forms will be administered to children from 8 to 17 years of age. Parallel parent proxy forms will be administered for children aged from 5 to 17 years. The short forms consists of 8 items using a 5-point Likert scale format (i.e. 1=unable to do, 5=can do without any difficulty). Raw scores are converted to a T–score, which is based on reference data from the US general population, where mean=50, standard deviation (SD)=10. The 2 forms take approximately 2 to 3 minutes to complete.

In the adult cohort, a separate newly developed Physical Function Short Form 8c 7-day scale will be used.

CONFIDENTIAL AND PROPRIETARY 67 of 183

8.1.3.4 Patient's global impression of symptom severity

The PGIS instrument is a single-item scale that evaluates the patient's symptom severity (separate single items for tumour pain, overall pain and tumour-related problems) at different points in time. Global impression of symptom severity will be measured by asking the subject or parent to best describe how his/her symptoms are on a 6-point scale (0=no symptoms, 1=very mild, 2=mild, 3=moderate, 4=severe, 5=very severe).

The PGIS instrument will be parent-reported for children aged up to 17 years and self-reported for children aged 8 to 17 years and adults.

8.1.3.5 Patient's global impression of change

The PGIC instrument is a single-item scale that evaluates the subject's perspective of changes in their tumour pain, overall pain and tumour-related problems. It has been used in several research studies on chronic pain in adults and more recently children (Arnold et al 2011; Mohammad et al 2014), and has been recommended by the IMMPACT for clinical studies involving chronic pain (Dworkin et al 2005; McGrath et al 2008).

An adapted version of the PGIC instrument will be used in this study at all visits except baseline (it should not be given pre-study because it assesses the perceived change from baseline). A parallel parent proxy form will also be used. On the adapted PGIC, subjects (and their parents separately) will give their overall impression of change of the child's: 1) tumour pain, 2) overall pain, 3) tumour-related problems from before initiation of selumetinib to the current evaluation point.

PGIC will be parent-reported for children aged up to 17 years and self-reported for children aged 8 to 17 years and adults.

8.1.3.6 Administration of COAs

Baseline eCOAs should be completed at the site on Cycle 1 Day 1 before dosing using an eCOA site tablet. Thereafter, subjects should complete the eCOAs at the site at scheduled visits. A web-based system will be used if the device is not available.

All assessments should be completed according to the following parameters:

- Without assistance from site staff or anyone else and according to the study SoA. However, if the subject has difficulties reading, the site staff can read the instructions to the subject.
- Before any other study procedures are conducted at a given visit
- Before being seen by a study nurse or physician

Each study center must allocate the responsibility for the administration of the COAs to a specific individual (e.g., a research nurse or study coordinator) and, if possible, assign a backup person to cover if that individual is absent.

The investigator will arrange for relevant training in the set-up of the site tablet and train subjects in how to respond to the eCOAs. The significance and relevance of the COA data should be explained carefully to subjects so that they are motivated to respond.

The following guidelines should be followed:

- The following order for completion should be ensured (and the eCOA tablet should be programmed accordingly):
 - Pediatric cohort: FLACC or Faces Pain Scale (depending on age), PII, PROMIS Mobility, PROMIS Upper Extremity, PedsQL, PGIS, PGIC
 - Adult cohort: NRS-11, PII, PROMIS Physical Function, EORTC-QLQ-C30, PlexiQoL, PGIS, PGIC
- eCOA completion must be done by the subject in private and site staff should ensure that subjects have a quiet place to complete the assessments.
- Throughout the study, subjects will continue filling in the same age-specific versions of the instruments as they completed at baseline.
- In the adult cohort, responsible physician will select the target tumor for which subjects will assess the pain intensity. The target tumor will be selected from a prespecified list of body locations on the eCOA tablet before subjects start doing the assessments.
- The research nurse or appointed site staff must explain to subjects the value and relevance of study participation and inform them that these questions are being asked to find out, directly from them, how they feel. The research nurse or appointed site staff should also stress that the information is confidential. Therefore, if the subjects have any medical problems, they should discuss them with the doctor or research nurse separately from the eCOA assessment.
- The research nurse or appointed site staff must train the subject on how to use the eCOA device, using the materials and training provided by the eCOA vendor.
- The research nurse or appointed site staff should remind subjects that there are no right or wrong answers.
- The research nurse or appointed site staff must avoid clarifying items to avoid bias.
- The adult subject must not receive help from relatives, friends, or clinic staff to respond to the eCOAs. However, site staff is allowed to read instructions to subject if subject have difficulties reading.

The research nurse or appointed site staff must monitor compliance to ensure all data is captured.

CONFIDENTIAL AND PROPRIETARY 69 of 183

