- ^{aa} Following screening, all eligible subjects will first receive a single oral dose of selumetinib 25 mg/m² (Cycle 0). After a period of 2 days, oral selumetinib 25 mg/m² twice daily (approximately every 12 hours) will be administered continuously for 28-day cycles (starting at Cycle 1) with no rest periods between cycles. Selumetinib will be dispensed after all assessments have been performed and the next 28-day cycle will begin at that point. Subjects will therefore be required to attend the site monthly to receive selumetinib. Selumetinib must be taken on an empty stomach (no food or drink other than water for 2 hours before and 1 hour after dosing) with water only.
- ^{bb} Subjects will receive a drug diary to record the specific time each dose was taken and to record reasons for any missed doses.

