Following the screening period (Day -28 to Day -1), all eligible subjects will first receive a single oral dose of selumetinib 25 mg/m^2 (Cycle 0). After a period of 2 days, oral selumetinib 25 mg/m^2 twice daily (approximately every 12 hours) will be administered continuously for 28-day cycles (starting at Cycle 1) with no rest periods between cycles. Subjects should be instructed to take the dose of selumetinib on an empty stomach (no food or drink other than water for 2 hours before and 1 hour after dosing) with water only. The capsules cannot be crushed and must be swallowed whole.

CONFIDENTIAL AND PROPRIETARY 23 of 183

Dosing will be performed based on body surface area (BSA) calculated by the equation below, and doses will be rounded to the nearest 5 to 10 mg using a dosing nomogram. BSA should be calculated at screening and every tumour assessment visit. The dose of selumetinib will be capped at 50 mg when BSA is \geq 1.9 m². At follow-up evaluations during tumour assessment visits, the dose of selumetinib will be adjusted for changes in BSA according to the dosing nomogram.

*For paediatric subjects with a body weight \leq 30 kg:

BSA (m^2) = body weight (kg) × 0.035 + 0.1

*For paediatric subjects with a body weight \geq 30 kg:

BSA $(m^2) = 1.15 + (body weight [kg] - 30) \times 0.02$

For all adult subjects:

BSA $(m^2) = 0.0061 \times \text{height} (\text{cm}) + 0.0128 \times \text{body weight} (\text{kg}) - 0.01529$

*For paediatric subjects the BSA calculation was refer from China National Formulary (Chemicals and Biological Products for Children) 2013 version.

Subjects will continue to receive selumetinib until disease progression or unacceptable drug-related toxicity, whichever occurs first. All subjects will be evaluated for safety and efficacy at a regular basis, as defined in Table 1.

The 30-day safety follow-up visits will be conducted at 30 days post-last dose/end of treatment for both paediatric and adult cohorts. Long-term post-treatment safety follow-up assessments will be conducted for 1 year (at 6- and 12-months post-treatment) for paediatric subjects only.

For subjects who discontinue study treatment due to reasons other than disease progression, tumour assessments will continue for approximately 1 year, if clinically applicable, and the assessment schedule should continue per the regular tumour assessment interval.

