Subjects will be administered a single oral dose of selumetinib 25 mg/m² at Cycle 0 Day 1. During the following 2--day washout period, intensive PK samples will be collected before and after this first single dose until pre-dose at Cycle 1 Day 1. From Cycle 1 Day 1, subjects will be administered multiple doses of selumetinib 25 mg/m² twice daily (BID) on a continuous schedule (28 days per cycle). The dose of selumetinib will be capped at 50 mg when body surface area (BSA) is ≥ 1.9 m². Intensive PK samples will be collected on Cycle 1 Day 8 for assessment of the 12-hour PK profile at steady state. Subjects need to be hospitalised for intensive PK sampling during the single dose period (from Cycle 0 Day -1 to Cycle 0 Day 2) and on Cycle 1 Day 8 during the multiple dose period.

Subjects will continue to receive selumetinib until disease progression or unacceptable drugrelated- toxicity, whichever occurs first. Selumetinib will be dispensed after all assessments have been performed and the next 28-day cycle will begin at that point. Subjects will therefore be required to attend the site monthly to receive selumetinib. Subjects will receive a drug diary to record the specific time each dose was taken and to record reasons for any missed doses.

All subjects will be evaluated for safety and efficacy at a regular basis, as defined in Table 1.

Safety assessments (clinical chemistry, haematology, urinalysis, physical examination, vital signs, height and weight, ECG, echocardiogram, ophthalmologic assessment, Tanner stages and performance status) will be performed at screening and at the end of each cycle up to the end of Cycle 4, every 2 cycles up to the end of Cycle 12, every 4 cycles up to the end of Cycle 24, and every 6 cycles thereafter, as long as the subject remains on study treatment. Pregnancy tests will be performed at screening and at the end of each cycle. AEs will be collected from the time of signing the informed consent form (ICF), throughout the treatment

CONFIDENTIAL AND PROPRIETARY 35 of 183

period and including the follow-up period. Safety assessments will also be performed at other visits during Cycles 0 and 1, as detailed in Table 1

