Unless clinically indicated otherwise, tumour assessments, as measured by 3D volumetric magnetic resonance imaging (MRI) of the target and nontarget PN, will be obtained at screening and every 4 cycles (16 ± 1 weeks) relative to the date of first dose for the first 2 years (24 cycles). From the end of Cycle 24, tumour assessments will be performed every 6 cycles (24 ± 1 weeks) as long as the subject remains on study treatment or until disease progression. Disfigurement assessments will be performed at screening and then at the end of Cycles 8, 16 and 24 as long as the subject remains on study treatment.

Clinical outcome assessments will be performed at screening and at the end of each cycle up to the end of Cycle 4, every 2 cycles up to the end of Cycle 12, every 4 cycles up to the end of Cycle 24, and every 6 cycles thereafter, as long as the subject remains on study treatment.

An end of treatment visit will be performed for subjects who permanently discontinue study treatment for any reason (except for death, lost to follow-up or withdrawal of consent).

The 30-day safety follow-up visit will be conducted at 30 days post-last dose/end of treatment for both paediatric and adult cohorts. Long-term post-treatment safety follow-up assessments will be conducted for 1 year (at 6 and 12 months post-treatment) for paediatric subjects only.

For subjects who discontinue study treatment due to reasons other than disease progression, tumour assessments will continue for approximately 1 year, if clinically applicable, and the assessment schedule should continue per the regular tumour assessment interval.

To minimise bias, tumour assessments will be determined by independent central review according to Response Evaluation in Neurofibromatosis and Schwannomatosis (REiNS) criteria (PR defined as a PN volume decrease of $\geq 20\%$ compared to baseline).

Refer to Table 1 for a comprehensive list of study assessments and their timings.

4.1.1 Study Conduct Mitigation During Study Disruptions Due to Cases of Civil Crisis, Natural Disaster, or Public Health Crisis

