8.1.3 Clinical outcome assessments (COAs)

COAs, an umbrella term referring to all outcomes and symptoms, can be reported directly by the subject (patient-reported outcomes), by a clinician (clinician-reported outcomes) or by an observer (observer-reported outcomes). In the current study, both patient-reported outcomes and observer-reported outcomes will be used. COA will be measured in accordance with Table 1. Copies of each of the assessments used are included in Appendix I.

Baseline clinical outcome assessments should be performed prior to and as close to the first dose of selumetinib as possible (PGIC should not have any baseline assessments). Post-baseline assessments should be performed at the end of each cycle up to the end of Cycle 4, every 2 cycles up to the end of Cycle 12, every 4 cycles up to the end of Cycle 24, and every 6 cycles thereafter, as long as the subject remains on study treatment. Clinical outcome assessments will be performed electronically using on-site tablets.

Clinical outcome evaluation questionnaire	Respondent	Relevant PN morbidity at enrolment	Age
FLACC	Parent/guardian-reported	All PN	3 years
Faces pain scale	Self-reported	All PN	4 to 17 years
NRS-11	Self-reported	All PN	Adults
PII	Self-reported Parent/guardian-reported	All PN	8 to 17 years Adults 5 to 17 years
Pain medication survey	Self-reported on paper in the adult cohort and Parent/guardian-reported on paper in the paediatric cohort	All PN	All subjects
PedsQL	Self-reported Parent/guardian-reported	All PN	5 to 7 years 8 to 12 years 13 to 17 years 3 to 4 years 5 to 7 years 8 to 12 years 13 to 17 years
EORTC QLQ-C30	QLQ-C30 Self-reported		Adults

Table 8Overview of eligible subjects completing clinical outcome
assessment questionnaires, by age of patient and respondent

CONFIDENTIAL AND PROPRIETARY

Clinical outcome evaluation questionnaire	Respondent	Relevant PN morbidity at enrolment	Age
PlexiQoL	Self-reported	All PN	Adults
PROMIS (mobility)	Self-reported Parent/guardian-reported	All PN	8 to 17 years 5 to 17 years
PROMIS (upper extremity function)	Self-reported Parent/guardian-reported	All PN	8 to 17 years 5 to 17 years
PROMIS (Physical Function – Short Form 8c 7-day)	Self-reported	All PN	Adults
PGIS	Self-reported Parent/guardian-reported	All PN	8 to 17 years Adults Up to 17 years
PGIC	Self-reported Parent/guardian-reported	All PN	8 to 17 years Adults Up to 17 years

Table 8Overview of eligible subjects completing clinical outcome

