9.5 Statistical analyses

Analyses will be performed by AstraZeneca or its representatives. A comprehensive statistical analysis plan (SAP) will be developed and finalised before database lock and will describe the subject populations to be included in the analyses, and procedures for accounting for missing, unused, and spurious data. This section is a summary of the planned statistical analyses of the primary and secondary endpoints. Any deviations from this plan will be reported in the CSR.

Same DCOs would be applied for both analysis of pediatric cohort and adult cohort. Primary DCO in this study will take place when the last subject dosed has had the chance to complete their visit at the end of cycle 10. Final DCO will occur when the last subject dosed has had the chance to complete their visit at the end of cycle 24. In addition, an interim analysis will be conducted when last subject dosed has had the chance to complete their visit at the end of cycle 4 to assess PK, safety, tolerability and efficacy in Chinese subjects with NF1 and inoperable PN.

Data from the paediatric and adult cohorts will be analysed separately. In general, baseline is defined as the last assessment before the first dose of selumetinib. Demographic data and baseline subject characteristics will be analysed for the safety analysis set. PK will be analysed based on the PK analysis set. Efficacy, clinical outcome assessment, exposure and safety data will be analysed based on the safety analysis set.

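### Section 8.1.3.6 puts the baseline tablet questionnaires on Cycle 1 Day 1, two days after the first selumetinib dose, against Table 1, Section 8.1.3 and Section 9.5

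*Protocol*

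**What the plan says.** The protocol places the first questionnaire assessment at three different times.

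- **Cycle 1 Day 1.** Section 8.1.3.6, on administration of the questionnaires: "Baseline eCOAs should be completed at the site on Cycle 1 Day 1 before dosing using an eCOA site tablet".
- **Before the first dose.** Section 8.1.3, repeated in Table 1 footnote v: "Baseline clinical outcome assessments should be performed prior to and as close to the first dose of selumetinib as possible". Table 1 marks every clinical outcome assessment except PGIC under Cycle 0 Day 1, with no mark at screening or at Cycle 1 Day 1.
- **Screening.** Section 4.1: "Clinical outcome assessments will be performed at screening and at the end of each cycle up to the end of Cycle 4".

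For the analysis, Section 9.5 states: "In general, baseline is defined as the last assessment before the first dose of selumetinib".

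The dosing sequence is not in doubt. Table 1 footnote aa: "Following screening, all eligible subjects will first receive a single oral dose of selumetinib" in Cycle 0, and then "After a period of 2 days, oral selumetinib" starts twice daily at Cycle 1. Section 4.1 confirms the order, since the first intensive PK samples are taken "before and after this first single dose until pre-dose at Cycle 1 Day 1".

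**The concern.** On Cycle 1 Day 1, an assessment made before dosing precedes the first twice-daily dose but follows the first selumetinib dose. It therefore cannot be a baseline under Section 9.5.

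The pain, quality-of-life and physical-function results for most tablet instruments are to be summarised as change from baseline. If a site takes the baseline only when 8.1.3.6 says, those changes are either undefined or computed from a post-dose value. An analysis plan can choose which recorded value to call baseline, but it cannot recover a pre-dose answer that was never collected. If some sites follow Table 1 and others follow 8.1.3.6, the reference point also differs between sites, in cohorts of about 16 subjects each.

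**Working it through.** **Step 1. Reproduce the calendar in Table 1.**

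- Cycle 0 Day 1 (single dose) = study day 1.
- After the 2-day period, Cycle 1 Day 1 = 1 + 2 = study day 3, as Table 1 shows.
- Check: Cycle 1 Day 8 = 3 + 7 = study day 10, and Cycle 1 Day 28 = 3 + 27 = study day 30. Both agree with Table 1.

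**Step 2. Place each baseline time against the first dose.**

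| Source | Time of baseline | Study day | Doses already taken | Meets Section 9.5? |
|---|---|---|---|---|
| Table 1, footnote v, Section 8.1.3 | Cycle 0 Day 1, pre-dose | 1 | 0 | Yes |
| Section 4.1 | Screening | −28 to −1 | 0 | Yes |
| Section 8.1.3.6 | Cycle 1 Day 1, pre-dose | 3 | 1 | No |

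The gap for 8.1.3.6 is 3 − 1 = 2 days, about 48 hours after one dose.

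**Step 3. Identify the instruments affected.** The sentence concerns the electronic assessments. Among these, the protocol fixes a change from baseline for:

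- FLACC (9.4.4.1.1, 9.5.4.1.1) and Faces (9.4.4.1.2, 9.5.4.1.2)
- NRS-11 (9.5.4.1.3) and PII (9.5.4.1.4)
- PedsQL (9.5.4.2.1) and EORTC QLQ-C30 (9.5.4.2.2)
- PROMIS (9.5.4.3, which names the mobility and upper extremity scores)

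Four instruments fall outside:

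- The pain medication survey is on paper (8.1.3.1.5).
- PlexiQoL is listed individually, with no change score fixed (9.5.4.2.3).
- PGIS is reported as counts and percentages (9.5.4.4).
- PGIC has no baseline by design.

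**Step 4. Recall period.** For an instrument with a 7-day recall, about 2 of the 7 days on Cycle 1 Day 1 fall after the first dose. They include the Cycle 0 sampling, which has 10 time points running to 30 hours post-dose (Table 12).

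**The case against.** The strongest reply is that the protocol already answers the timing question. Section 8.1.3.6 itself tells sites to follow the schedule of assessments. Section 8.1.3 refers to Table 1, and the general text ahead of Section 8.1 makes adherence to Table 1 a requirement. Only one sentence is out of line, and a site following Table 1 has a valid baseline. This limits how far the error is likely to reach, but it does not remove it. Section 8.1.3.6 then points to two different days, and its explicit visit name is what a site or tablet vendor might implement.

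It is also fair that Section 4.1 is a weaker conflict. Screening is pre-dose, so a screening questionnaire would satisfy Section 9.5 although it departs from Table 1.

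The wording of Section 9.5, which gives its definition as a general rule, does not rescue 8.1.3.6. Footnote v and Section 8.1.3 set the same rule specifically for these assessments.

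A reader might infer three stronger claims that the document does not support.

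- **That every change score is lost for all 32 subjects (16 + 16).** That is a ceiling, reached only if every site follows this sentence and disregards Table 1. The protocol does not show how sites acted or how the tablets were programmed.
- **That every questionnaire is affected.** Step 3 above shows that four are not.
- **That baseline pain is inflated, so that improvement appears spuriously.** This is conceivable for items asking about worst pain over the past week, given the blood sampling. But no figure supports it, and an early benefit from one dose would bias the other way. Hospitalisation begins on Cycle 0 Day −1, so a correctly timed baseline also includes part of the stay. The main adult NRS-11 outcome concerns the target tumour, which sampling should not directly affect, and not every instrument uses a 7-day recall.

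**Conclusion.** The contradiction is real: Section 8.1.3.6 sets a baseline two days and one dose too late by the protocol's own definition. For a subject assessed only at that time, the seven instruments named in step 3 have no protocol-valid baseline, and the reference day may vary between sites.

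The consequence is conditional. It depends on a site following 8.1.3.6 instead of Table 1 and holding no screening questionnaire. The number of subjects affected, and the direction and size of any bias, are unknown; the effect of a single dose two days earlier may be small.

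The endpoints concerned are secondary and analysed descriptively, in an open-label study that tests no hypothesis. Safety, PK and tumour response are untouched. This should be fixed, because a missed pre-dose assessment cannot be recovered, but it does not undermine the study's primary objectives.

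**What to change.** 1. In Section 8.1.3.6, set the baseline electronic assessments on Cycle 0 Day 1, before the single dose.
2. In Section 4.1, replace screening with the same time for these assessments, so that it agrees with Table 1.
3. Check the tablet visit programming and the completion timestamps of baseline questionnaires already collected.
4. Flag any baseline completed on Cycle 1 Day 1 as post-dose, so that it is not silently treated as meeting Section 9.5.

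The cost is two sentences in the protocol, a note to sites and a data check. No visit or assessment is added: Table 1 already schedules these questionnaires on Cycle 0 Day 1, and subjects are already in hospital then.
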